MORS-SF is a 14 item instrument which measures a parent's 'representations' of their infant's thoughts, feelings and intentions towards them. The instrument comprises two scales: 'warmth' and 'invasion', which are calculated and reported separately, and therefore form two separate co-primary outcomes in this evaluation. 'Warmth' measures the parent's model of their infant's emotional warmth towards them. It is obtained from statements such as 'my baby smiles at me' and 'my baby likes doing things with me'. 'Invasion' measures the parent's model of their infant's emotional invasion or control over them (or in other words, it measures the level by which the parent experiences their infant as disruptive and invasive), and is obtained from statements such as 'my baby annoys me' and 'my baby wants too much attention' (see Appendix A for all 14 statements). As such both scales provide a measure of the parent's relationship with the baby.

Both scales have a total possible score of 35. A score of 11 or less on the warmth scale should indicate concern. Concern on the invasion scale is indicated by a score of over 17.

Karitane Parenting Confidence Scale (KPCS)¹²

The Karitane Parenting Confidence Scale is a 15 item instrument which measures perceived parental-self efficacy (PPSE) - perceptions of confidence with regard to the parenting role. This scale will be used to provide an estimate of impact for the first co-secondary outcome consistent with the outcome 'improved parental confidence' identified as important in the development of the theory of change/logic model.

The KPCS is scored by summing across all responses with the possible range of scores being 0-45. The cut-off score is 39, such that parents scoring 39 or less may be experiencing low levels of parenting confidence.

Parental Stress Scale (PSS)¹³

The Parental Stress Scale is an 18 item instrument measuring parental stress - a parent's perceived stress relating to the parenting role. This scale will provide a measure of the 'lower parental stress' outcome identified through the logic model/theory of change process. A number of items are reverse scored, and scores are summed to give an overall score in the range 18-90. Higher scores indicate higher levels of perceived parental stress.

CSC 'step-up'

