- **Imputed sample at analysis (bounds)** – We propose to obtain estimates using extreme bounds for the two co-primary outcomes. With this approach sample missing values are imputed using two different approaches. In these data, missing values at the baseline for both approaches are imputed using mean imputation with a missing value indicator derived for each sample case for which baseline imputation is

¹⁴ What Works for Children's Social Care (2021). 'What Works for Children's Social Care Randomised Controlled Trial Statistical Analysis Guidance.'
<https://whatworks-csc.org.uk/wp-content/uploads/WWCSA-RCT-Statistical-Analysis-Guidance-V1.1-1.pdf>

conducted. Two samples are then created. In the first sample, missing follow-up values for the intervention sample are set at the maximum value for the observed distribution at follow-up for the outcome. Conversely, for the control group, missing values are set to the minimum value of the observed distribution. A second data set is then created where missing values in the intervention group are set to the minimum value and in the control group to the maximum value. The primary analysis is then conducted on both data sets. The results give a feel for the possible range of plausible treatment effect estimates, from a maximum plausible estimate to a minimum estimate. The wider this range the greater the degree of caution that should be exercised in the interpretation of sample estimates in the presence of appreciable levels of missing data.

Primary Analysis

The purpose of the primary analysis is to provide estimates of the average effect of intention to treat (AITT) – that is the average effect of the offer of VIG to members of the study intervention sample on the co-primary outcomes at follow-up. The estimator from which sample estimates of AITT are obtained is chosen on the basis that the trial is multi-site by design and that sites are a convenience sample. For all analyses, sites are treated as fixed effects, consistent with the requirements set out in the funder’s Statistical Analysis Guidance¹⁵.

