imputed datasets for each primary outcome as appropriate and results compared to the completed cases analysis.

If multiple imputation does not appear to perform satisfactorily, then we propose to first estimate a drop out model where the probability of missingness at follow-up is modelled on the basis of a full set of variables derived from the referral form and captured at baseline, in a logistic regression. Variables that appear to be associated with missingness at follow-up will be added to the regression model [1] as additional covariates, and the model re-estimated on the completed cases at analysis sample file.

Given that there are no wholly satisfactory approaches to addressing the situation where missing data are suspected to be MNAR experimentally, our assessment of the potential consequences of missing data for our analysis of the co-primary outcomes (MORS-SF) will conclude with estimation of extreme bounds on the sample estimates of AITT (Gerber, Alan & Green, Donald, 2012; Puma et al., 2009). Under this approach we make no assumption about the missing data process. First we propose to conduct mean imputation for missing baseline observations with dummy variables indicators for dyads with a missing value on X at the baseline. Then an upper bound on AITT will be calculated through imputing missing outcomes at follow-up for the control group at the minimum value for the outcomes concerned at their site, whilst for the intervention group imputing missing values set to the maximum value for the relevant outcome at their site. A lower bound AITT can be obtained by imputing missing values for the control group on the relevant outcome at follow-up equal to the maximum observed value at their site, whilst for the intervention group the minimum observed value. If the range between the upper and lower bound is quite large this tells us to exercise a high degree of caution in relation to results from the completed cases analysis.

Secondary Analysis

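### The extreme-bounds analysis is given two fill rules, and both use observed extremes, so the claim that it makes no assumption about missing data is not true

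*Protocol*

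**What the plan says.** The Protocol describes the bounds analysis in two places.

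- **Analysis Plan, list of samples, item on the imputed sample (bounds).** In the first data set, "missing follow-up values for the intervention sample are set at the maximum value for the observed distribution at follow-up for the outcome", and "for the control group, missing values are set to the minimum value of the observed distribution". The second data set reverses the arms. No site is mentioned. The purpose is put modestly: "The results give a feel for the possible range of plausible treatment effect estimates". A wider range is to be read as a reason for more caution.
- **Primary Analysis, Missing data and imputation.** The upper bound is obtained by "imputing missing outcomes at follow-up for the control group at the minimum value for the outcomes concerned at their site" and, in the intervention arm, by "imputing missing values set to the maximum value for the relevant outcome at their site". For the lower bound, control dyads receive a value "equal to the maximum observed value at their site"; the matching clause for the intervention arm gives the observed minimum and does not repeat the site. This text follows a remark that no approach deals fully with MNAR data, and it says: "Under this approach we make no assumption about the missing data process". A large gap between the bounds again calls for caution.

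The limits of the scale are in the document. Under Outcome Measures, "Both scales have a total possible score of 35". Appendix A gives seven items per scale, each scored 0 to 5 and summed, so the possible range is 0 to 35.

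**The concern.** Both places describe the same analysis: the same outcomes, mean imputation of baseline with a missing indicator, and opposite extremes in the two arms. Two analysts who each followed one of them would report different bounds.

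Both rules also take the fill value from responders. That assumes no non-responder lies outside the range seen among responders, which is an assumption about the missing-data process. If the parents with the most extreme scores are the ones who do not reply, the process itself cuts off the observed range, and the rule then treats the cut-off range as the limit. The assumption is strongest under the site rule at BANES and Hounslow, where Table 3 implies about 15 follow-up responders each.

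The width of the bounds is what the plan reads from this analysis. An ambiguous width that can only err on the narrow side understates how far missing outcomes could move the result.

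**Working it through.** **Inputs from the Protocol.** Table 3: 252 randomised, 141 responding at both waves, 25 at follow-up only. Follow-up responders by site: Achieving for Children 67 + 12 = 79, Stockport 47 + 8 = 55, BANES 13 + 2 = 15, Hounslow 13 + 2 = 15. Allocation is 1:1 within site. Scale range 0 to 35.

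**Inputs assumed.** The Protocol gives no mean or SD for MORS-SF in this population. Means from 10 to 31 and SDs from 4 to 8 were tried, with normal scores rounded and capped at 0 and 35.

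**Step 1: the plan's response figures.** 252 × 0.80 = 201.6 baselines; 201.6 × 0.70 = 141.1 at both waves; (252 − 201.6) × 0.50 = 25.2 at follow-up only. These agree with 202, 141 and 25. Missing at follow-up: 252 − 166 = 86, or 34.1%. Summing the site rows gives 41 + 29 + 9 + 9 = 88, or 34.9%; the difference is rounding. The Protocol states no width for the bounds, so there is none to reproduce.

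**Step 2: width formula.** For an unadjusted difference in means,

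width = (missing share in intervention + missing share in control) × (fill maximum − fill minimum).

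With equal arms of 126, the two shares sum to 86/126 = 0.683 however the missing dyads split between arms.

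**Step 3: scale limits.** 0.683 × 35 = 23.9 points (86 missing), or 88/126 × 35 = 24.4 points (88 missing).

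**Step 4: observed extremes.** Mean widths over 4,000 simulated samples at the site counts above (88 missing, equal missingness by arm). The site rule weights each site's range by its number missing. Shortfall is measured against 24.4.

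| Assumed mean, SD | Pooled width | Site width | Shortfall, pooled | Shortfall, site |
|---|---|---|---|---|
| 31, 4 | 10.3 | 9.0 | 58% | 63% |
| 27, 5 | 15.0 | 13.3 | 39% | 45% |
| 10, 5 | 16.3 | 14.4 | 33% | 41% |
| 27, 7 | 18.7 | 16.5 | 23% | 32% |
| 10, 7 | 20.1 | 17.8 | 18% | 27% |
| 22, 7 | 22.0 | 19.6 | 10% | 20% |
| 17.5, 8 | 24.3 | 22.4 | under 1% | 8% |

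The site rule is 1.3 to 2.4 points narrower than the pooled rule. All four sites observed both 0 and 35 in at most 0.05% of samples. The pooled sample did so in at most 16%, except at mean 17.5 and SD 8, where it did in 89%.

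**Step 5: effect of covariate adjustment.** A separate simulation with equation [1], mean-imputed baseline and a missing indicator, at mean 25 and SD 5, gave 14.2 (site), 16.0 (pooled) and 24.0 (scale limits). Adjustment leaves the scale-limit width almost unchanged and keeps the order of the three.

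**The case against.** The case on the other side has four parts.

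- **The two statements may be summary and detail.** The first never says pooled, and the list it belongs to points ahead to a fuller discussion. The site version can be read as the operative rule. This is fair, but nothing says that the second replaces the first, and the second itself drops the site in its last clause. Settling on the site rule would also leave the narrower of the two.
- **The claim may concern the mechanism only.** The Protocol uses missing-data process to mean MAR or MNAR, so the sentence could mean just that no mechanism is assumed. This does not rescue it. Non-response by the most extreme parents is an MNAR mechanism, and the rule excludes it.
- **No conclusion changes.** This largely stands. The primary estimate comes from completed cases, with multiple imputation next and the bounds last. Width is read qualitatively, with no threshold. Even the narrowest case above, 9.0 points at SD 4 or 2.25 SD, is about five times the stated MDES of 0.44 SD, so every version calls for caution.
- **Scale limits are harsh.** They put every missing parent in one arm at the floor and every one in the other at the ceiling, and the width then depends almost only on the response rate. That is so, and it is the price of a bound without assumptions. It is a fair reason to report an observed-range version as well.

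A reader might go further and infer that the bounds are certain to be too narrow, by a third or more. The documents do not support that: they give no mean or SD, and with widely spread mid-scale scores the pooled rule loses almost nothing.

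**Conclusion.** The point holds in two parts. The fill rule is stated in two ways that give different bounds, and neither has the property the Protocol claims for it. Both rules give bounds that can never be wider than scale-limit bounds and are narrower unless responders span 0 to 35. Under the site rule that exception is close to impossible at the planned counts; under the pooled rule it is possible.

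At the Table 3 response rates the scale-limit width is about 24 points. The shortfall is roughly 0 to 58% under the pooled rule and 8 to 63% under the site rule. These percentages rest on the assumed means and SDs, capped normal scores, and an unadjusted difference; the direction does not depend on the assumed means and SDs.

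A reader might also infer that the trial's main result is compromised, or that an observed-range analysis has no place. Neither follows. The matter is confined to a sensitivity analysis, and an observed-range version is acceptable if it is labelled for what it is.

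**What to change.** State one rule, in the same words, in the sample definition and in Missing data and imputation: missing follow-up MORS-SF scores are set to 0 or 35 at all sites, in opposite directions by arm, and then reversed. The no-assumption sentence can then stay, attached to that version.

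If an observed-range version is also reported, define it once as pooled or by site, label it as observed-range, and do not describe it as free of assumptions.

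The cost is wording in two places and a one-line change in code. The downside is that the reported bounds become wider.

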3. What is the difference in the average level of parental self-efficacy among focal parents with a child 12 months or less in age and with a social worker, in dyads randomised to receive Video Interaction Guidance, compared to focal parents in dyads randomised to control (business as usual) conditions?
4. What is the difference in the average level of parental stress among focal parents with a child 12 months or less in age and with a social worker, in dyads randomised to receive Video Interaction Guidance, compared to focal parents in dyads randomised to control (business as usual) conditions?
5. What is the probability that a focal child aged 12 months or less and with a social worker in dyads randomised to receive Video Interaction Guidance, 'steps down' from being a child-in-need (CiN) or on a child protection plan (CPP) over a three month period subsequent to the intervention, to being on a CPP if they were not already, or becoming a CLA (child who is looked after), or pre-proceedings are initiated,

compared to focal children in dyads randomised to control (business as usual) conditions over the same period?

Design

Trial type and number of arms		Pragmatic multi-site trial with two arms
Unit of randomisation		Parent-infant dyad
Stratification variables (if applicable)		Site
Primary outcome(s)	Variable	- Representation – ‘warmth’ - Representation – ‘invasion’
	Measure (instrument, scale)	- Mothers Object Relations Short Form (MORS-SF) – warmth - Mothers Object Relations Short Form (MORS-SF) – invasion
Secondary outcome(s)	Variable(s)	- Parental self-efficacy - Parental stress - CSC Step-up
	Measure(s) (instrument, scale)	- Karitane Parenting Confidence Scale - Parental Stress Scale - Whether a focal child status changes from CiN to CPP, CPP to CLA, or pre-proceedings were initiated (indicators combined to form a binary outcome with constituent measures obtained from social care records)

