The impact study design is a pragmatic, multi-site, effectiveness trial, with parent-infant dyads allocated to intervention and control within sites, at random, on a 1:1 basis. As a result, dyads are randomised within sites, which are local authorities, and the resulting data are clustered by site. Outcomes are recorded for the focal parent and focal child within dyads. There are four sites in total, with family dyads identified within each site by local intervention coordinators and then randomised to treatment and control using a randomised permuted block approach described more fully below.

Trained social workers are responsible, after training and discussions with Babies 1st, for identifying all eligible dyads that meet the inclusion criteria (with the exception of those for whom exclusion criteria apply), completing a referral form for each dyad and administering consent procedures. The referral form contains the following information:

- Focal parent’s contact details
- Focal parent’s age
- Focal child’s age
- Focal child’s gender
- Focal child subject to formal multi-disciplinary planning process (i.e. CP, CiN, Early Help Plan)?
- Other children in the household subject to formal multi-disciplinary plan?
- Ethnicity
- Focal parent’s care history
- Focal parent has other children taken into care?
- Does the focal parent smoke?

- Current accommodation
- Age focal parent finished full-time education
- Focal parent currently suffers from anxiety
- Focal parent currently suffers from depression
- Focal parent's alcohol consumption

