Once referral and consent procedures are complete, details of each dyad are passed to IFF Research, who check the completeness of the referral form data and confirm eligibility (that the dyad meets the study inclusion criteria). Subsequently, IFF administer a baseline questionnaire to the focal parent. The baseline questionnaire contains the following measures, details of which can be found in Appendix A: MORS-SF, Karitane Parenting Confidence Scale, Parental Stress Scale. For the sample randomised between July and November 2021, child protection outcomes (CiN, CPP, CLA and initiation of pre-proceedings) are collected from administrative case data held by the local authorities and further details provided later in this section. Full details of the measures included within the baseline questionnaire, along with the justification for their choice, and the reliance on self-completion questions rather than observations, is provided in the section entitled 'Outcome measures' below.

The respondent (focal parent) is expected to be the focal child's mother but may be the father where he is the only, or primary, care giver. Dyads are given two weeks to complete the questionnaire. It is important to note, that the study's funders have decided that all dyads that meet the study inclusion criteria and who provide their consent should be randomised, regardless of whether a complete baseline questionnaire is received. This means that some missing data, either item or unit (dyad) missing, can be expected at baseline. The evaluators in partnership with Babies 1st and the study sites will take a number of steps to limit non-response or missingness at baseline, such as telephone reminders to non-respondents, telephone support for focal parents to complete the questionnaire, and support for social workers and VIG Practitioners to support and encourage parents to participate.

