Data on the third co-secondary outcome will be obtained from social services administrative case data obtained from LAs by IFF Research and linked to the trial data set in pseudonymised form. The outcome will be a binary response coded to '1' if the focal child in a dyad is observed to have had a 'step up' outcome. By step-up outcome we mean that there is a new CPP in place (where none-existed previously, i.e. the focal child was CiN), or a CLA, or pre-proceeding have been initiated in relation to the focal child. For a dyad to be coded to '1' a new CPP must have materialised in the six months since randomisation, or the onset of a CLA occurred over this period, or pre-proceeding initiated. If none of these events occur the outcome is coded to '0'. Only data for the dyads randomised between July and

¹¹ Oates, J., Gervai, J., Danis, I., Lakatos, K. and Davies, J. (2018) 'Validation of the Mothers' Object Relations Scales Short-Form (MORS-SF)', *Journal of Prenatal and Perinatal Psychology and Health*, vol. 33, pp. 38-50.

¹² Črnčec, R., Barnett, B., & Matthey, S. (2008). *Karitane Parenting Confidence Scale: Manual*. Sydney South West Area Health Service. Sydney: Australia.

¹³ Berry, J. O., & Jones, W. H. (1995). 'The Parental Stress Scale: Initial psychometric evidence. *Journal of Social and Personal Relationships*', 12, 463-472.

November 2021 will be included in analyses of this indicator, such that a period of six months since randomisation could elapse within the time scales for this trial. If the timescales for the trial are extended, then more of the study sample will be included in this analysis.

Correcting for multiple comparisons

In line with WWCSA's statistical analysis guidance¹⁴ (p.11) no correction for multiple comparisons will be made (this is a two arm trial and there are less than four outcomes in each category – primary and secondary).

Analysis Plan

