Here we allow for the effects of the intervention to vary across sites through the inclusion of a treatment by site interaction term. This specification permits us to test whether imbalances between intervention and control groups by site resulting from attrition, should they emerge, affect our sample estimates. We propose to obtain a sample average estimate by taking a weighted average of the site specific effects obtained from this model as follows:

$$\hat{\beta}_{IToT} = \sum_{J=1}^J \frac{N_J}{N} \hat{\beta}_k$$

Where $\frac{N_J}{N}$ is the proportion of the total sample at site J . The standard distributional assumptions regarding ε_{ij} are made. A weighted average of the standard error will also be formed in a similar manner. Site specific standard errors will be obtained using bootstrap procedures based on 500 replications. Inference on $\hat{\beta}_{IToT}$ will be performed through constructing frequentist 95 percent confidence intervals.

The second form of sensitivity analysis for the two primary outcomes involves an extension to model [1] above. It is proposed to include a full range of covariates in an extended regression analysis. Alongside a baseline measure of the dependent variable and site specific dummy variables we propose to obtain a sample estimate of AITT from a regression equation including additional covariates capturing:

- focal parent's age,

- baby's age in months; and
- presence of a partner

This analysis will test the sensitivity of the results to the specification of the regression equation and choices made over the inclusion of various covariates.

Missing data and imputation

As previously mentioned, one major challenge for this study will be missing data at both baseline and follow-up for the first two of the three co-primary outcomes derived from survey questionnaires (as well as secondary outcomes). In other words, obtaining unbiased estimates of AITT from the estimator represented by equation [1] above will likely be compromised by both unit and item non-response where estimates are obtained from fitting the statistical model to the completed cases sample file.

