Secondary analysis will consist of two sets of distinct analysis: first the derivation of sample estimates of the average effect of intention to treat on (1) parental self-efficacy (Karitane Parenting Confidence Scale); (2) Parental stress (Parental Stress Scale); and (3) the step-up/CSC escalation binary indicator. Second, for the primary analyses discussed above, for both co-primary outcomes, sample estimates of complier average causal effects (CACEs) will be obtained if it has proved possible to collect accurate take-up measures for individual dyads

Sample estimates of AITT for self-efficacy and parents stress will be obtained from fitting regression models to the relevant data consistent with the Equation [1] above, and using the same statistical procedures, where the dependent variables 'Y' and covariate 'X' are derived from the relevant scales and questionnaire data at baseline and follow-up. All model estimates will be derived from the completed cases sample files for the relevant data items.

A sample estimate of AITT for the step-up binary outcome will also be obtained as part of the secondary analysis. Sample estimates will be obtained from a linear probability model containing the following covariates, where the binary response is the dependent variable:

- Focal parent's age at randomisation (from the referral form)
- Focal baby's age in months at randomisation (from the referral form)
- Whether the father is present in the family home at randomisation (from the referral form)

The analysis will be performed on sample cases for those dyads randomised between July and November 2021. We anticipate that this sample will comprise some 150 cases. This analysis should not be affected by missingness. For binary outcomes, effect sizes will be reported as differences in adjusted incident rates.

If possible we will seek to obtain records on programme exposure for each dyad, whether allocated to intervention or control. If such indicators are of sufficient reliability and quality we propose to obtain complier average causal effects on the co-primary outcomes (Glennester & Takavarasha, 2013).

Exploratory Analysis

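### The step-up model names a covariate with no documented source and leaves out the collected baseline plan status; research question 5 uses a different window from the outcome definition

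*Protocol*

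**What the plan says.** **Model.** Secondary Analysis states: "Sample estimates will be obtained from a linear probability model containing the following covariates, where the binary response is the dependent variable". The list is focal parent's age, baby's age in months, and "Whether the father is present in the family home at randomisation (from the referral form". All three are attributed to the referral form. The analysis set is dyads randomised from July to November 2021, expected to number about 150, and the section says missing data should not affect it.

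**Data sources.** Design introduces the form with "The referral form contains the following information" and lists fifteen items. One of them is "Focal child subject to formal multi-disciplinary planning process (i.e. CP, CiN, Early Help Plan". For the other baseline source it says: "The baseline questionnaire contains the following measures, details of which can be found in Appendix A: MORS-SF, Karitane Parenting Confidence Scale, Parental Stress Scale".

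**Outcome.** The CSC 'step-up' section codes a child 1 if, within six months of randomisation, "there is a new CPP in place (where none-existed previously, i.e. the focal child was CiN", or the child becomes looked after (CLA), or pre-proceedings start. The Summary and Design give the same six months.

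**Question.** Research question 5 describes the child as stepping down "over a three month period subsequent to the intervention" and then lists a new CPP, CLA and pre-proceedings.

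**Related model.** The extended regression under 'Sensitivity analysis – primary outcomes' adds "presence of a partner" and names no source for it.

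**The concern.** Three parts of the step-up analysis do not fit together.

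1. A covariate is credited to a form that, as listed, does not hold it. A household item that is not asked at referral is hard to recover later with the same timing for every dyad.
2. Equation [1] adjusts each questionnaire outcome for its own baseline. Step-up has a natural baseline too, the child's plan at entry, and the form already records it. The model does not use it, and randomisation is stratified by site only, so chance imbalance in plan status is not controlled by design or by analysis.
3. The research question and the outcome definition start the clock at different points. Escalations during delivery count under one and not under the other.

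At stake is a clear, fittable analysis of the one trial outcome that parents do not report themselves.

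**Working it through.** The protocol gives no step-up rate, no CiN/CPP split and no power figure for this outcome, so there is no stated number to reproduce. Parts 1 and 3 compare sections. Part 2 is an illustration.

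**1. Source of the covariate**

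- The fifteen listed items are: contact details, parent's age, child's age, child's gender, child's plan, other children's plans, ethnicity, parent's care history, other children in care, smoking, accommodation, age at leaving education, anxiety, depression and alcohol. None records a father, partner or other household adult. The accommodation item, as listed, does not say who lives there.
- Appendix A gives the items of the three questionnaire scales. The nearest is Karitane item 9, which asks about confidence in a partner's support, not about presence in the home.
- If the item were moved to the questionnaire, Table 3 expects 202 of 252 returns, so 50/252 = 20% would be missing. On 150 dyads that is about 30, which would not fit the statement that missingness is no issue here.

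**2. Baseline plan status**

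Participants admits children on CiN or CPP. Routes to a code of 1:

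| Plan at entry | New CPP | CLA | Pre-proceedings |
|---|---|---|---|
| CiN | counts | counts | counts |
| CPP | cannot count | counts | counts |

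Inputs: n = 75 per arm (150 at 1:1, from the protocol). Assumed: CiN share s = 0.5, step-up rate a = 0.25 for CiN and b = 0.10 for CPP.

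- Overall rate: p = sa + (1−s)b = 0.125 + 0.05 = 0.175
- Variance explained: R² = s(1−s)(a−b)² / [p(1−p)] = 0.25 × 0.0225 / 0.1444 = 0.039
- SE of the unadjusted risk difference: √[p(1−p) × 2/n] = √(0.1444 × 2/75) = 0.062
- Effect of adjustment on the SE: √(1−0.039) = 0.98, a cut of about 2%
- SD of the between-arm difference in plan share: √[s(1−s) × 2/n] = √(0.25 × 2/75) = 0.082
- Shift from a 10-point imbalance: 0.10 × 0.15 = 1.5 points, about a quarter of the SE
- Shift from a 2-SD imbalance: 0.163 × 0.15 = 2.4 points, about 0.4 of the SE

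Range under other assumed values, with CiN share 30–70%:

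| Assumed rates | R² | Cut in SE | Shift at 10-point imbalance | SE |
|---|---|---|---|---|
| CiN 20–40%, CPP 10% | 1.5–12% | about 1–6% | 1–3 points | 5.5–7.6 points |
| CiN 10%, CPP 20% | 1.5–2% | about 1% | 1 point, opposite sign | 5.5–6.1 points |

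**3. Window**

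Interventions puts delivery at 3–4 months, and Design expects it to start very soon after randomisation. In months since randomisation:

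- Outcome definition: 0 to 6
- Question 5: 3 to 6 (3-month delivery) or 4 to 7 (4-month delivery)

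The end points nearly coincide. The start points differ by three to four months.

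**The case against.** **Plan status is optional.** Randomisation protects the estimate without it, the documents give no rates, and even the direction of the gap is unknown: children already on a CPP have fewer countable events but start at a higher tier. This stands. A reader might infer that the omission biases the result, or that plan status is the strongest predictor; the documents support neither. What they do establish is that status limits which events can count.

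**Site is covered.** A reader might infer from the covariate list that site has been left out. Primary Analysis says sites are fixed effects in all analyses, and the list omits the treatment indicator too, so it is plainly not the whole model.

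**The direction is a slip.** A reader might infer that question 5 asks about de-escalation. The events in the same sentence are all escalations, and the rest of the protocol says step-up. Only the label is wrong.

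**Controls have a period.** A reader might infer that a post-intervention window has no meaning for controls. Question 5 says they are compared over the same period, which partly answers this. The start still depends on when delivery ends, which is not a date that control dyads have.

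**The partner covariate may have a source.** The sensitivity section does not credit it to the referral form, and Design lists the questionnaire's measures without saying there is nothing else in it. So it is not shown that the sensitivity model cannot be fitted, only that no source is documented. The step-up covariate is different: its source is named, and the listed content does not include it.

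**Conclusion.** The point holds as three repairs of unequal weight.

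- The father covariate cannot be obtained from its stated source as the protocol lists it. This is a contradiction within the document and needs no assumption. Dropping the covariate would leave the intention-to-treat estimate valid.
- Adding plan status is a free improvement of modest size: about 4% of variance and a 2% smaller SE under assumed rates of 25% and 10%, or 1.5–12% and about 1–6% across the assumed range. It also guards against chance imbalance. It does not correct a bias.
- The window conflict is substantive at its start point, because escalations in the first three to four months count under the outcome definition and not under question 5. The wording about stepping down is a slip.

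All of this concerns one of three secondary outcomes and one sensitivity model. The main models for the co-primary outcomes are untouched, and no stated figure changes.

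**What to change.** 1. In Secondary Analysis, add baseline plan status (CiN vs CPP, from the referral form) to the step-up model, alongside parent's age, baby's age and the site fixed effects that Primary Analysis already requires.
2. Choose one course for the household covariate and apply it to both models. Either add a single father/partner-in-household item to the referral form, with one definition in place of the present two (father in one section, partner in the other), or delete the covariate from the step-up model and from the extended sensitivity model. Collection is only worthwhile if the item is in place for all referrals.
3. Reword research question 5 as the probability of a step-up within six months of randomisation, in both arms.

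The cost is protocol wording, plus one tick-box on the form if the covariate is kept. Sample size and follow-up do not change.
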